	
 • A helminth parasitic infection within 6 months prior to the date informed consent is obtained. • Tuberculosis requiring treatment within the 12 months prior to screening. • Known primary immunodeficiency disorder.
Investigational medicinal products	
Tralokinumab
 
 • Tralokinumab is a human recombinant monoclonal antibody of the immunoglobulin G4 (IgG4) subclass that specifically binds to human interleukin (IL) 13 and blocks interaction with the IL-13 receptors. • Active substance: tralokinumab. • Dosage form: solution (in accessorised pre-filled syringe, 1.0 mL fill volume). • Concentration: 150 mg/mL. • Dose: 300 mg every 2 weeks (Q2W) following an initial loading dose of 600 mg • Method of administration: Subcutaneous (SC). 
Placebo
 
 • Placebo contains the same excipients in the same concentration only lacking tralokinumab.
Auxiliary medicinal product (AxMP)	
TCS (Europe: Class 3 [potent])
 
Mometasone furoate, 0.1% cream provided in kit sizes of 180–225 g every 2 weeks.

Duration of treatment	
Each subject's trial participation will be up to 46 weeks, divided into a screening period (including washout, if applicable) of up to 6 weeks, a treatment period of 26 weeks, and a follow-up period of 14 weeks.
 
Eligible subjects may be invited to enter a long-term extension trial conducted under a separate protocol (LP0162-1337, ECZTEND). Subjects who transfer to ECZTEND must have had their last visit in the treatment period (Week 26 under the current protocol).

Number of subjects	A total of 250 subjects will be randomised 1:1 to treatment with tralokinumab 300 mg+TCS or placebo+TCS.
Number and distribution of trial sites	Up to 40 clinical sites in Europe are anticipated. Distribution between countries will be based on feasibility. Inclusion of subjects from Germany is prioritised.

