8.2 Inclusion criteria

For inclusion into this trial, subjects must fulfil all of the following criteria:

1. Signed and dated informed consent has been obtained prior to any protocol-related procedures.
2. Age 18 and above.
3. Diagnosis of AD as defined by the Hanifin and Rajka (1980) criteria for AD ([21](#); [Appendix 4](#))
4. History of AD for ≥ 1 year.
5. Subjects who have a recent history (within 1 year before the screening visit) of inadequate response to treatment with topical medications.
 - Inadequate response is defined as failure to achieve and maintain remission or a low disease activity state (comparable to IGA 0=clear to 2=mild) despite treatment with a daily regimen of TCS of medium to higher potency (\pm TCI as appropriate), applied for at least 28 days or for the maximum duration recommended by the product prescribing information (e.g., 14 days for super-potent TCS), whichever is shorter.
 - Subjects with documented systemic treatment for AD in the past year are also considered as inadequate responders to topical treatments and are potentially eligible for treatment with tralokinumab after appropriate washout.

6. AD involvement of $\geq 10\%$ body surface area at screening and baseline according to component A of SCORAD.
7. EASI score ≥ 20 at screening and baseline
8. An IGA score of ≥ 3 at screening and at baseline
9. A Worst Daily Pruritus numeric rating scale (NRS) average score of ≥ 4 during the week prior to baseline.
 - Worst Daily Pruritus NRS score at baseline will be calculated from daily assessments of worst itch severity (Worst Daily Pruritus NRS) during the 7 days immediately preceding randomisation (Day -6 to 0). A minimum of 4 Worst Daily Pruritus NRS scores out of the 7 days is required to calculate the baseline average score. For subjects who do not have at least 4 scores reported during the 7 days immediately preceding the planned randomisation date, randomisation should be postponed until this requirement is met, but without exceeding the 6 weeks' maximum duration for screening.
10. Subjects must have applied a stable dose of emollient twice daily (or more, as needed) for at least 14 days before randomisation.
11. Women of child-bearing potential must use a highly effective* form of birth control (confirmed by the investigator) throughout the trial and at least for 16 weeks (5 half-lives) after last administration of IMP.

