14.1 Sample size

With a significance level of 5%, a sample size of 250 subjects will provide 99% power for detecting a treatment difference for the primary endpoint, assuming an EASI75 response rate at Week 16 of 40% vs 15% for tralokinumab+TCS and placebo+TCS, respectively. Assuming a response rate of 30% vs 15% in reduction of Worst Daily Pruritus NRS (weekly average) score of at least 4 from baseline to Week 16 for tralokinumab+TCS and placebo+TCS, respectively, the trial will provide at least 80% power for rejecting the hypotheses related to the primary endpoint and the secondary endpoint evaluating pruritus at Week 16.

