When building the 100 complete data sets, available data from all subjects will be used, excluding individual subject data captured after initiation of rescue treatment, permanent discontinuation of IMP, or subject-onset of the COVID-19 pandemic.

Once the 100 complete data sets have been generated by MI, non-responder imputation of relevant data points not affected by the COVID-19 pandemic will be applied according to the rules described above.

For each of the resulting 100 complete data sets, the difference in response rates between treatment groups will be analysed using the Mantel-Haenszel risk difference stratified by prior CSA use (yes/no) and baseline disease severity (IGA 3 or 4). The estimates and standard errors from the 100 analyses will be pooled to one estimated treatment difference and associated standard error using Rubin's rule to draw inference. From these pooled estimates, the 95% CI for the treatment difference will be calculated.

Sensitivity analysis for the primary estimand

A tipping-point analysis will be performed with the purpose of assessing the robustness of results of the primary analysis (for the primary estimand) with respect to the MAR assumption for missing data due to the COVID-19 pandemic.

The tipping-point analysis will only test the MAR assumption among subjects in the tralokinumab+TCS group who had missing data imputed at the Week 16 visit due to subject-onset of the COVID-19 pandemic or data missing due to the COVID-19 pandemic. The tipping-point analysis will assess how severe the departure from the MAR assumption in the tralokinumab+TCS group has to be in order to impact the results (i.e. to change the

conclusion of the primary analysis of the primary estimand) from significant to non-significant.

The tipping-point analysis will be performed using the MAR imputed Week 16 data from the primary analysis of the estimand. For each of the 100 imputed datasets, a quantity Δ will be added to all imputed Week 16 values for subjects in the tralokinumab+TCS group who have had subject-onset of the COVID-19 pandemic prior to Week 16 or have data missing due to the COVID-19 pandemic at Week 16, thereby causing the imputed values to be 'shifted' by Δ ($\Delta = 0$ implies MAR).

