14.3.9 Analysis of secondary endpoints

The secondary endpoints evaluate the impact of 16 and 26 weeks of treatment on (i) itch, (ii) severity and extent of AD, and (iii) HRQoL. The corresponding endpoints are (i) reduction (yes/no) of Worst Daily Pruritus NRS average score for the past week (hereinafter ‘Worst Daily Pruritus NRS weekly average’) of at least 4 from baseline to Week 16/ Week 26, (ii) the change from baseline to Week 16/ Week 26 in SCORAD, the (iii) change from baseline to Week 16/ Week 26 in DLQI score, (ii) IGA score of 0 (clear) or 1 (almost clear) at Week 16/ Week 26, (ii) EASI75 at Week 26. Worst Daily Pruritus NRS over the last week prior to baseline (Day -6 to 0) will be used to calculate the baseline itch (see also inclusion criterion no. 9).

EASI75 at Week 26 is a binary endpoint and it will be analysed as described for the primary endpoint (EASI75 at Week 16) using all 4 estimands with the modification that the imputation algorithm will be applied until Week 26.

Reduction of Worst Daily Pruritus NRS weekly average of at least 4 from baseline to Week 16/ Week 26 is a binary endpoint, and it will be analysed as described for the primary endpoint (EASI75 at Week 16) using all 4 estimands with the modification of the ANCOVA imputation model that reduction of Worst Daily Pruritus NRS weekly average replaces EASI where preceding values are used as covariates. Only subjects with an average Worst Daily Pruritus NRS score of 4 or above at baseline will be included in these analyses.

For each of the binary secondary endpoints, tipping-point analyses using the method described for the tipping-point analyses of the binary primary endpoint (EASI75 at Week 16) will be added as sensitivity analyses for the primary estimand.

Subgroup analysis of binary endpoints

Subgroup analyses will be applied for the primary analyses of the primary and tertiary estimands for the groups: sex, prior CSA use (yes/no), baseline disease severity (IGA 3 or 4),

country (Germany: yes/no), and baseline age (≤ 65 years, >65 years). Interaction between subgroups and treatment effect will be tested using a conditional logistic regression. The conditional logistic regression model will implement a test of the treatment-by-subgroup interaction while adjusting for the same strata used in the corresponding analyses. The model used for the test of interaction will be:

$$Y = \text{treatment} + \text{subgroup} + \text{treatment} * \text{subgroup}$$

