14.3.16 General principles

Unless otherwise stated, all significance tests will be 2-sided using the 5% significance level. All CIs will be presented with 95% degree of confidence. An observed-cases approach will be used for tabulations of data by visit (i.e. involving only those subjects who attended each specific visit).

Categorical data will be summarised using the number and percentage of subjects in each category and treatment group. Continuous data will be summarised using the mean, median, standard deviation, 1st quartile, 3rd quartile, minimum, and maximum values.

All the analyses specified in the protocol will be reviewed in relation to the blinded data actually obtained and the statistical analysis plan and the analysis set definition document will be finalised before breaking the randomisation code.

Any changes from the statistical analysis planned in this clinical trial protocol will be described and justified in a protocol amendment, the statistical analysis plan, and/or in the CTR dependent on the type of deviation.

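### The pruritus responder comparison leaves out baseline itch, forgoing a small and uncertain gain in precision on a valid test with about 81% power

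*Protocol*

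**What the plan says.** Protocol section 14.3.9: "Reduction of Worst Daily Pruritus NRS weekly average of at least 4 from baseline to Week 16/ Week 26 is a binary endpoint". The same paragraph sends the endpoint to the EASI75 analysis under all four estimands. The change it makes is to the imputation model, where earlier itch values take the place of earlier EASI values. It also restricts the analysis to subjects whose baseline average is 4 or higher.

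For the primary estimand (Protocol section 14.3.8.1), each imputed data set is "analysed using the Mantel-Haenszel risk difference stratified by prior CSA use (yes/no) and baseline disease severity (IGA 3 or 4"), and the results are pooled by Rubin's rule. SAP section 6.6.3.1 follows the protocol and defines the weekly averages. It adds no baseline-itch term to the comparison.

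Baseline itch is always available, because inclusion criterion 9 (Protocol section 8.2) requires "A Worst Daily Pruritus numeric rating scale (NRS) average score of ≥ 4 during the week prior to baseline". The scale ends at 10.

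On power, Protocol section 14.1 says that "the trial will provide at least 80% power for rejecting the hypotheses related to the primary endpoint and the secondary endpoint evaluating pruritus at Week". The visit meant is Week 16, and the assumed rates are 30% against 15%. No other secondary endpoint has a stated power.

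The continuous secondary endpoints are treated differently: their repeated measurements model includes the baseline score by visit (Protocol section 14.3.9.1).

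**The concern.** The definition of response ties it to where a subject starts. A subject at baseline 4 must reach 0 to respond, while a subject at 10 need only reach 6. If response does vary with baseline itch, chance imbalance in baseline itch between arms adds noise that a covariate already collected could remove. Baseline IGA rates skin signs, so it is at best a partial substitute.

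Precision matters more here than for EASI75. The endpoint is in the confirmatory hierarchy, and under Protocol section 14.3.6 a failed test stops every test placed after it. Its power is also close to the stated floor, whereas EASI75 has power to spare.

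**Working it through.** **Inputs from the documents.** "With a significance level of 5%, a sample size of 250 subjects will provide 99% power" for EASI75 (section 14.1). Tests: "all significance tests will be 2-sided using the 5% significance level" (section 14.3.16). Allocation: "A total of 250 subjects will be randomised 1:1 to treatment with tralokinumab 300 mg+TCS or placebo+TCS" (synopsis), so 125 per arm. EASI75: "assuming an EASI75 response rate at Week 16 of 40% vs 15% for tralokinumab+TCS and placebo+TCS". Pruritus response at Week 16: 30% against 15% (section 14.1). No dropout allowance is stated.

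**Step 1: reproduce the plan's power.** Power = Φ[(d − 1.96·SE0)/SE1], with SE0 from the pooled rate and SE1 from the separate rates.

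- Pruritus: d = 0.15. SE0 = √(2 × 0.225 × 0.775/125) = 0.0528. SE1 = √((0.30 × 0.70 + 0.15 × 0.85)/125) = 0.0520. Then (0.15 − 0.1035)/0.0520 = 0.894, so power is 81.4%. Unpooled variance gives 82.3%, and the exact chi-square test 81.7%.
- EASI75: d = 0.25, SE0 = 0.0565, SE1 = 0.0542. Then (0.25 − 0.1107)/0.0542 = 2.57, so power is 99.5%.
- Both endpoints: 0.995 × 0.814 = 81.0% if independent, and at least 80.9% whatever the dependence.

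The stated figures hold without any covariate. The pooled formula needs 121 per arm for 80%, so 125 leaves little slack.

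**Step 2: what adjustment could add.** If baseline itch explains a share R² of the within-arm response variance, both standard errors shrink by about √(1 − R²). The documents give no value for R², so it is an assumption throughout.

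| R² | Power | Gain (points) |
|---|---|---|
| 0 | 81.4% | 0 |
| 2% | 82.2% | 0.8 |
| 5% | 83.4% | 1.9 |
| 8% | 84.5% | 3.1 |
| 10% | 85.3% | 3.9 |

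**Step 3: which R² is plausible.** Baseline itch was simulated as normal, truncated to 4–10. Three change models were calibrated to 30% and 15% response.

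| Assumed mean, SD before truncation | Change model | R², active / placebo | Power |
|---|---|---|---|
| 7.7, 1.4 | Absolute drop unrelated to baseline | 0 / 0 | 81.4% |
| 7.7, 1.4 | Proportional drop | 4.7% / 3.1% | 83.0% |
| 7.7, 1.4 | Regression to the mean | 5.0% / 3.7% | 83.2% |
| 7, 1.8 | Absolute drop unrelated to baseline | 0 / 0 | 81.4% |
| 7, 1.8 | Proportional drop | 8.1% / 5.3% | 84.2% |
| 7, 1.8 | Regression to the mean | 6.8% / 5.0% | 83.8% |

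**Step 4: check with the proposed estimator.** In 4,000 simulated trials per setting, a standardised logistic risk difference was compared with the unadjusted one. The unadjusted test used unpooled variance, so it starts slightly above 82%.

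| Odds ratio per SD of baseline itch | Unadjusted | Adjusted |
|---|---|---|
| 1.0 | 82.6% | 82.4% |
| 1.5 | 82.3% | 83.6% |
| 1.8 | 82.7% | 85.1% |
| 2.7 | 82.5% | 86.6% |

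The gains are −0.2, 1.3, 2.4 and 4.1 points. The first is within simulation error, so an irrelevant covariate costs practically nothing.

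**Step 5: the non-responder rule.** Under the primary estimand, rescue, permanent discontinuation and missing data not due to COVID-19 all count as non-response. These outcomes are not decided by the itch score, so they dilute its link with response. A separate set of runs (baseline mean 7–8, SD 1.3–2) gave gains of 0 to 2.6 points. With an assumed 20% of subjects set to non-response, the maximum fell to about 2.1. It fell to about 1.5 if rescue or discontinuation was also assumed likelier at high baseline itch.

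**The case against.** The strongest reply is that nothing is broken. The Mantel-Haenszel test is valid, its type I error does not depend on this choice, and the plan's power claim holds as written. All of that stands.

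The sponsor could add that EASI75, IGA 0/1 and pruritus all share one stratified method, and that a single method for the binary family is a legitimate choice. That also stands. A reader might infer an inconsistency from the baseline adjustment in the continuous models, but the documents do not show one: binary and continuous endpoints are simply analysed by different conventions.

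Third, baseline-adjusted itch analyses already exist. Change and percent change in the pruritus score are pre-specified among the other endpoints and use the repeated measurements model (Protocol section 14.3.10). They are useful support, but they target a hypothetical estimand and lie outside the testing hierarchy, so they add no precision to the responder test.

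Fourth, the two estimators need not weight strata alike. If risk differences vary across strata, a standardised risk difference can differ slightly from the Mantel-Haenszel one. That is a fair cost. It limits the case for the change but does not remove it.

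**Conclusion.** The observation is correct and its consequence is small. Baseline itch is collected, is likely to predict response, and is unused in the comparison. Using it would add about 0 to 4 power points to 81.4%, most likely 1 to 3. The range rests on assumed baseline distributions and change models, because the documents supply neither. A high non-response rate from rescue or discontinuation pushes the gain down, and an absolute drop unrelated to baseline makes it nil.

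Three stronger readings should be resisted.

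- A reader might infer that the endpoint is underpowered or mis-analysed. It is neither on the plan's own inputs.
- A reader might assume a correlation of 0.5 between baseline itch and response and reach 91.0% power. That means R² = 25%, about three times the largest value in step 3, and nothing in the documents supports it.
- A reader might infer that a miss here would cost many later endpoints. The rule in section 14.3.6 is clear, but the order is in Panel 12, whose figure is not in the text reviewed. How many endpoints follow is unknown.

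This is an inexpensive improvement to offer the sponsor, not a defect to be corrected.

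**What to change.** Before unblinding, add to SAP section 6.6.3.1, for the pruritus responder endpoints at Weeks 16 and 26 under the primary estimand:

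1. In each imputed data set, after the non-responder step, fit a logistic model with treatment, prior CSA use, baseline IGA and baseline pruritus score (continuous).
2. Derive the marginal risk difference by standardising over the analysed subjects, with a delta-method or robust standard error.
3. Pool over the 100 data sets by Rubin's rule.
4. Keep the planned Mantel-Haenszel risk difference as the sensitivity analysis. Name it also as the fallback if the model does not converge, since SAP section 6.6.3.1 already reports possible convergence problems with the logistic interaction tests.

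The cost is a paragraph of SAP text and standard code. No subject is lost, because the analysis already requires a baseline value. Protocol section 14.3.16 allows a justified change of this kind through the SAP. The price is a model-based estimate for this endpoint, with weighting over strata that may differ slightly from Mantel-Haenszel. If the sponsor prefers one method for all binary endpoints, a sentence saying so would be enough.

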7.2 Number of subjects needed

Assuming a screening failure rate of 25%, approximately 333 subjects will be screened and approximately 250 subjects will be randomly assigned 1:1 to tralokinumab 300 mg+TCS or placebo+TCS. Randomisation will be handled using the interactive response technology (IRT) to ensure continued blinding in the trial.

The statistical power considerations for this sample size are described in Section 14.1.

This trial will be conducted at approximately 40 sites in Europe. The anticipated minimum number of randomised subjects per trial site is 4 and the maximum number of subjects per trial site is 30.

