4. This stepwise procedure will then be repeated sequentially for the remaining visits starting with Week 6 until Week 16. The only modification is that the EASI values from the preceding 2 visits will be included as covariates in addition to baseline EASI, and prior CSA use and baseline disease severity as factors. The missing binary EASI75 response at Week 16 will be derived from the corresponding underlying imputed EASI value.

Analysis of Week 16 response

For each of the 100 complete data sets, the difference in response rates between treatment groups will be analysed using the Mantel-Haenszel risk difference stratified by prior CSA use (yes/no) and baseline disease severity (IGA 3 or 4). The estimates and standard errors from the 100 analyses will be pooled to one estimated treatment difference and associated standard error using Rubin's rule to draw inference. From these pooled estimates, the 95% CI for the treatment difference will be calculated.

Sensitivity analysis for the quaternary estimand

Rather than assuming that observations are MAR within each treatment group, it is assumed that missing data from subjects who had any of the intercurrent events in the tralokinumab+TCS group will resemble missing data from subjects from the placebo+TCS group who had none of the intercurrent events. The underlying assumption is that the effect of tralokinumab following rescue treatment, permanent treatment discontinuation, or subject-onset of the COVID-19 pandemic is similar to the effect of placebo. It should be noticed that

this assumption is pronouncedly conservative in favour of placebo as it tends to minimise the differences between treatment groups.

Imputation of missing data at Week 16 will be done using a pattern mixture model where missing data in the tralokinumab+TCS group as well as the placebo+TCS group will be imputed from observed data in the placebo+TCS group (using a so-called copy-reference approach). With this exemption, the stepwise MI procedure and subsequent analysis will be conducted in the same way as specified for the primary analysis of the quaternary estimand.

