### **6.6.4 Multiple imputation**

For the analysis of the primary and secondary endpoints, multiple imputation will be carried out, as specified in the protocol, using SAS PROC MI. Unless otherwise specified in the protocol or this SAP, the seed 11109946 will be used in any multiple imputation strategies.

When performing multiple imputation of continuous parameter values, imputed values outside the relevant parameter scale for visits prior to the relevant visit will be used as it is. Values imputed at the relevant visit will be truncated to the nearest upper or lower bound on the given scale. E.g., negative imputed EASI values at Week 16 will be set to 0 in an analysis of Week 16 data.

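### Read as written, the pruritus imputation model omits baseline Worst Daily Pruritus NRS and does not name the variable to be imputed

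*Protocol*

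**What the plan says.** For EASI75, protocol section 14.3.8.4 imputes the EASI score itself, visit by visit, and derives response from the imputed score. Two kinds of EASI term enter the model and are listed separately: from Week 6, "EASI values from the preceding 2 visits will be included as covariates in addition to baseline EASI". Section 14.3.8.1 uses the same procedure for the primary estimand.

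Section 14.3.9 applies this to the pruritus responder endpoints at Weeks 16 and 26, with the modification that "reduction of Worst Daily Pruritus NRS weekly average replaces EASI where preceding values are used as covariates". It restricts the analysis to subjects whose baseline average is at least 4. It names neither the imputed variable nor a baseline pruritus covariate.

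SAP section 6.6.4 adds no pruritus model. Its general rule is "Values imputed at the relevant visit will be truncated to the nearest upper or lower bound on the given scale"; earlier visits are left untruncated. SAP section 6.6.3.1 drops the tipping-point analysis that protocol section 14.3.9 had planned for this endpoint.

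For SCORAD and DLQI (protocol 14.3.9.1 and 14.3.9.2) the imputation models that are written out include the baseline of the score being imputed.

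**The concern.** The endpoint is defined against the subject's own baseline itch, so baseline NRS determines how much improvement a response requires. A model without it treats subjects with the same earlier reductions alike, whether they began at 4.5 or at 9. It can also fail under the missing-at-random assumption the plan relies on, if missingness depends on baseline itch.

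Pruritus response at both weeks belongs to the hierarchically tested secondary endpoints (protocol 14.3.6), and the Week 16 endpoint carries the second power statement in section 14.1. With the tipping-point analysis gone, no planned sensitivity analysis of the primary estimand would show an error in this model.

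**Working it through.** **1. The plan's power figures.** Inputs: "With a significance level of 5%, a sample size of 250 subjects will provide 99% power"; "all significance tests will be 2-sided using the 5% significance level"; 1:1 allocation (protocol 7.2), so 125 per arm; 40% vs 15% for EASI75; "Assuming a response rate of 30% vs 15% in reduction of Worst Daily Pruritus NRS". Power = Φ{[Δ − 1.96·√(2p̄(1−p̄)/n)] / √[(p₁q₁+p₂q₂)/n]}.

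- EASI75: (0.25 − 1.96×0.0565)/0.0542 = 2.57, power 99.5%.
- Pruritus: (0.15 − 1.96×0.0528)/0.0520 = 0.89, power 81.4%.
- Both: 0.995×0.814 = 81.0% if independent; at least 99.5 + 81.4 − 100 = 80.9% under any dependence.

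The stated 99% and at least 80% are reproduced. They do not involve the imputation model, so this point does not alter them.

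**2. What the substitution reaches.** Section 14.3.8.4 separates preceding-visit EASI from baseline EASI. The substitution in 14.3.9 is confined to the first. Literally, baseline EASI stays and baseline NRS is absent.

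**3. Why baseline matters.** From a baseline of 4.5, response means reaching 0.5 or less, a fall of 4/4.5 = 89%. From 9 it means reaching 5 or less, a fall of 4/9 = 44%.

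**4. Carrying reductions is not the fault.** Write B for baseline, Nₜ for NRS and Rₜ = B − Nₜ. With B in the model, regressing Rₜ on Rₜ₋₁, Rₜ₋₂ and B is a linear re-expression of regressing Nₜ on Nₜ₋₁, Nₜ₋₂ and B, and gives the same imputations. The missing term is B.

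**5. Effect by baseline itch.** Simulation of the stepwise imputation to Week 16, 200,000 per arm, calibrated to 30% and 15%. Assumptions not in the documents: baseline NRS limited to 4–10, mean 6.5 or 7.5, SD 1.5; 20% missing completely at random; prior CSA use and IGA factors omitted. Tralokinumab, baseline below 6, improvement proportional to baseline, reduction imputed, true rate 10–15%:

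| Last observed | Without baseline NRS | With baseline NRS |
|---|---|---|
| No post-baseline | 31% | 16–18% |
| Week 4 | 22–23% | 14–17% |
| Week 8 | 17–19% | 13–16% |
| Week 14 | 12–15% | 12–14% |

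If improvement is instead an absolute amount, the same stratum has a true rate of 30–31% and an imputed rate of 28–30%: no excess. If raw NRS is imputed from earlier reductions without baseline NRS, the direction reverses: imputed 0–13% against true 11–31%.

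**6. Effect on the treatment difference.** Bias = f × (imputed difference − true difference among imputed subjects), with f = 0.20 assumed. Examples with baseline mean 6.5 and absolute improvement:

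- Reduction imputed, no baseline NRS, no post-baseline data: 0.20×(13.8 − 15.1) = −0.3 points.
- Raw NRS from earlier reductions, no post-baseline data: 0.20×(3.6 − 15.9) = −2.5 points.
- The same, observed to Week 14: 0.20×(11.6 − 15.0) = −0.7 points.

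Across all these completely-at-random settings the bias is −0.3 to +0.2 points (reduction, no baseline NRS), −0.3 to +0.4 (reduction with baseline NRS) and −0.4 to −2.5 (raw NRS, no baseline NRS).

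With missingness commoner at low itch, proportional improvement and the reduction imputed (100,000 per arm, 20% missing), a true difference of 15.0 became 16.3 with no post-baseline data and 15.4 when observed to Week 4. Adding baseline NRS gave 15.0–15.2 and 15.0. Imputing raw NRS from earlier reductions gave 12.2–14.1, under proportional or absolute improvement.

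A further simulation covering both missingness patterns gave:

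- reduction imputed: no bias when missingness is completely random, and +0.1 to +0.9 points when it is commoner at low itch and improvement is proportional;
- raw NRS from earlier reductions: −0.5 to −2.3 points;
- with baseline NRS: within about 0.4 points in every scenario.

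The bias scales roughly with f. The 0.5–2.3 points at 20% become about 0.1–0.6 at 5% (multiply by 5/20).

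**7. Truncation.** Every analysed subject has B ≥ 4. An NRS draw below 0 that is cut to 0 gives a reduction of B ≥ 4, still a response. Status never changes.

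**The case against.** Section 14.3.9 says pruritus is handled like the primary endpoint, and that procedure uses the baseline of the score being imputed. An analyst could reasonably carry the substitution through to baseline pruritus. That reading is open, so it cannot be said that baseline NRS is excluded on every reading. What stands is that the words do not provide it.

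The reach in the tested estimand is also narrow. Section 14.3.8.1 turns other missing data, and data after rescue or discontinuation unrelated to COVID-19, into non-response; only COVID-19-related values keep their draw. Pruritus is a daily eDiary item, and subjects on home use are reminded to complete it (protocol Appendix 8). Onset through prolonged interruption cannot precede Week 6, since it is dated at the third missed dose or later (14.3.1). COVID-19-related discontinuation or rescue can come earlier, and data after onset are discarded even if collected. Nothing in the documents links COVID-19 disruption to baseline itch; without such a link, imputing the reduction leaves the arm difference about right. These limits hold. They do not rescue the raw-NRS reading, which is biased even under completely random missingness.

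A reader might go further and infer that using reductions is itself an error, or that impossible NRS values below 0 create false responders. Steps 4 and 7 show neither is so. Draws below 0 come from the normal model: they occur in 2–13% of low-itch tralokinumab imputations without baseline NRS and still in 1–11% with it.

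**Conclusion.** The point holds as a defect in the written model for a tested endpoint, of modest size. As worded, the model has no baseline-itch term and two possible imputed variables, and the consequences differ between them.

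- **Reduction imputed:** early-missing low-itch subjects are over-imputed if improvement is proportional to baseline (31/15 = 2.1 to 31/10 = 3.1 times the true rate below baseline 6 with no post-baseline data). High-itch subjects are under-imputed in compensation. The arm difference is inflated only if missingness also depends on baseline itch: about 0.1–0.9 points, up to 16.3 − 15.0 = 1.3 in the most adverse setting tried.
- **Raw NRS imputed from earlier reductions:** the difference is pulled towards zero by about 0.5–2.3 points at 20% missing (0.4–2.8 over all settings tried).

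These sizes rest on assumed baseline distributions, improvement patterns and missing fractions. The COVID-19-related share, which limits the effect in the primary estimand, is not given. The exposure is wider in the hypothetical estimand, where all missing and discarded values are imputed. The documents do not support a claim that the pruritus result will be materially inflated or that the power statement fails.

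**What to change.** In SAP section 6.6.4, write out the pruritus model: impute the weekly average Worst Daily Pruritus NRS (0–10) stepwise, with baseline Worst Daily Pruritus NRS in place of baseline EASI, the two preceding weekly averages as covariates, and the same factors as for EASI. Truncate to 0–10 at the analysed visit, then derive the reduction of at least 4. This also settles which scale the truncation rule refers to, since for a reduction the bound would be each subject's own baseline.

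The cost is wording and the matching program. Baseline NRS is already collected for inclusion criterion 9 and is required for the endpoint, so no subject is lost. The change reduces the low-itch excess without removing it entirely (16–18% against 10–15% with no post-baseline data), and it removes the dependence on how the sentence is read.
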